2.2 Trial Design

Randomised controlled trial.

Women aged 49-71 years attending for routine mammography screening will be randomised by batch/clinic to either standard care group (2DDM) or intervention group (DBT + S2D). The images will be double read by NHS BSP film readers fulfilling NHS BSP QA criteria for film reading and who have undergone training in DBT image interpretation. The results of film reading will be recorded on the National Breast Screening Computer System (NBSS) and then complete data (with surgical and pathology data where appropriate) will be downloaded for statistical analysis. The initial trial recruitment period will be the length of time required to reach the recruitment target of up to 70,000 women by 8 NHSBSP screening centres.

Interval cancer data will be collected as per routine by the screening centres in collaboration with Cancer Registries and QA Reference Centres.

2.3. Trial Strategy and Recruitment.

1. Recruitment.

Up to 09.2023, the trial has recruited over 36,000 women from 6 screening centres, randomized 1:1 between the control group (standard 2DDM) and the intervention group (DBT and 2DDM/synthetic 2D). Two further sites are starting recruitment this autumn – Leicester, St George’s London. We do not anticipate increasing the number of trial sites above 8.

The overall recruitment rate is just over 50% of those who attend screening and are invited to participate. The participation rate varies between the sites (26%-81%) and reflects differences in the local population demographics. Participation is higher at static sites compared to mobile screening sites. We have examined ways of increasing participation rates including

- different consent processes – face to face, phone and online;
- revision of the patient information materials;
- investment in staff time to facilitate consenting.

We estimate that trial recruitment will continue at between 1500 and 2000 per month with 8 recruiting sites.

2. Strategy.

We propose a strategy to ensure that there are sufficient numbers of women recruited to each arm of the trial in order to address the principal objectives of the trial and to ensure that the trial is completed and results available within the funding available, and within a reasonable timeframe in relation to ongoing discussions about application of new technology to the national screening programme.

3. Randomization ratio.

We have therefore considered changing the randomization ratio in favour of the intervention arm and decreasing the overall recruitment target. We conclude that the randomization ratio could be changed to 1:3 (control:intervention) and the overall target recruitment changed to 70,000. This would provide sufficient data to address the impact of DBT screening on interval cancer rates and cancer detection. We plan to augment the trial analysis with a further secondary analysis, comparing endpoints between our intervention group and figures from the national programme, using standardised incidence ratios.

Table 1. Estimate of numbers recruited in control and intervention groups to 03.2025, with a 1:3 randomization ratio from 01.2024

			Control	Intervention	Total
To 09.2023			18,000	18,000	36,000
To 12.23			20,000	20,000	40,000
01.24 - 03.25 @1:3	control	intervention			
1500/month	5625	16,875	25,625	36,875	62,500
2000/month	7500	22,500	27,500	42,500	70,000

4. Invasive cancer detection rates.

For a comparison of invasive detection rates (the first primary endpoint), if we posit 9 per thousand in the DBT arm and 7 in the control, we will have approximately 80% power with the totals assuming recruitment of 1,500 per month and in excess of 80% power with 2,000 per month (5% significance level, 2-sided testing). Thus even without the use of the routine screening data, we will have sufficient power for the first primary endpoints.

5. Interval cancer rates.

Assuming the national rate of interval cancers in the control group, 3.5 per 1000 over 3 years, and if we assume conservatively that the reduction is 25% less than the increase in invasive detection rates, we would anticipate a rate of 2 per 1000 in the intervention arm.

Our totals for recruitment of 1,500 per month would yield in excess of 90% power to detect this as significant (5% significance level, two-sided testing). Thus we will be powered for this too.

6. As noted above, we also propose to carry out age-standardised comparison of these endpoints with those observed nationally, since the latter give highly precise estimates of outcomes for usual care. However, we re-emphasise that the primary analyses will be the protocol-specified randomised trial comparisons.

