2.5 Economic analysis

Economic evaluation of DBT

We will undertake a detailed study of the cost of screening with 2DDM and with DBT and either S2D or 2DDM. Capital and maintenance costs related to screening technologies will be obtained from the manufacturers or finance departments at the screening centres and amortized appropriately according to predicted lifetime. Staff costs and overheads for screening centres and image reading centres will be derived from centre finance departments. The time taken to record images with each screening modality, and the time to read images will be determined and combined with centre costs to estimate a total cost per mammographic screen for each of the screening centres in the trial. Costs associated with follow-up of a positive screen will be determined in consultation with screening centres. Patient costs will be estimated on the basis of typical attendance times valued at average gross wage rate along with estimates of average travel costs.

We will undertake a cost-utility analysis of DBT + S2D (or 2DDM) compared to current practice (2DDM). The primary analysis will consider an NHS perspective and include future related costs of screening (diagnosis and treatment of Breast cancer). A societal perspective which includes patient costs of attending screening and follow-up will be examined in a sensitivity analysis. The primary analysis will consider the costs and consequences of Breast screening with either modality over the trial follow-up period. We will estimate the impact on health and treatment costs of cancers detected by predicting treatment costs and mortality according to age and prognostic factors at diagnosis. Mortality will be weighted for quality of life to estimate the Quality Adjusted Life-Years (QALYs) lost to Breast cancer in each arm. A QALY is measure of health outcomes which combines longevity and quality of life. If overall costs are higher in the DBT arm the data will be combined to estimate an Incremental Cost-Effectiveness Ratio (ICER) for DBT and allow comparison against accepted thresholds of £20,000 to £30,000 per QALY. The trial data will be bootstrapped (a resampling technique to quantify the impact of uncertainty in the data) and the results presented as a Cost-Effectiveness Acceptability Curve (CEAC). The CEAC plots the probability an intervention is cost-effective according to the value placed on the health outcome and after allowing for sampling uncertainty.

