4.1 Informed Consent Procedures

- All eligible women who are to be invited to participate in the trial will be sent written information about the trial. . This information will either be sent by post or emailed.
- The majority of potentially eligible women will be contacted by telephone prior to screening appointment, she will be asked whether she has received the written trial information and whether she is willing to participate in the trial.
- Women will be advised to read all the information including the consent form and make a decision of whether to participate prior to attendance for screening.

There are a number of options available for consenting as outlined below:

Option 1: e-consenting - Women receive the trial information and/or are contacted by a member of the PROSPECTS team. If a women decides that she would like to consent, she may visit the PROSPECTS website or go directly to the e-consenting portal URL (details of this are provided on the PIS). At the end of the consent form, there will be an option to enter an email address where a confirmation email and her consent form will be sent, alternatively she can contact the trial site to request a copy of the form to be posted. If personal electronic devices and the internet are not accessible, the e-consenting process may be possible by using a PROSPECTS iPad/Tablet at sites that have adequate time and space available to facilitate this. Women may contact the site if she requires assistance with this. If a women has e-consented less than 48 hours prior to her appointment, she must bring confirmation with her, as the list of those consented is exported in advance.

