4.2 Randomisation Procedures

All the participating screening centres will identify clinics which could be used for the trial. The clinics will be randomised in advance to either standard intervention 2SD and DBT.

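### Clinics or batches are randomised, but the stated powers are calculated as if women were randomised individually, and detection power at 1,500 per month has no reserve for clustering

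*Protocol*

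**What the plan says.** **Unit of randomisation.** Section 2.2 says that women "will be randomised by batch/clinic to either standard care group (2DDM) or intervention group (DBT + S2D"). Section 4.2 repeats this at clinic level: "The clinics will be randomised in advance to either standard intervention 2SD and DBT". The Introduction and section 4.1 also refer to a clinic randomisation process. The protocol does not say whether a batch and a clinic are the same thing.

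**Power.** For invasive detection, section 2.3 says "if we posit 9 per thousand in the DBT arm and 7 in the control, we will have approximately 80% power with the totals assuming" 1,500 recruits per month, and "in excess of 80% power with 2,000 per month (5% significance level, 2-sided testing"). For interval cancers it starts from the national figure: "Assuming the national rate of interval cancers in the control group, 3.5 per 1000 over 3 years". It expects 2 per 1000 in the intervention arm and concludes: "Our totals for recruitment of 1,500 per month would yield in excess of 90% power to detect this as significant". Section 3 repeats these statements. Section 2.4 adds a second-round comparison of 8 against 6 per 1000, with more than 80% power at 25,625 control and 36,875 intervention women.

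Each power statement rests on rates, numbers of women, a 5% level and two-sided testing. None mentions the size or number of clinics, an ICC or a design effect.

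**The concern.** When groups are randomised, outcomes within a group may be correlated. The effective sample size is then the number of women divided by a design effect of at least 1. A power figure calculated on independent women is an upper limit for such a design, and equals the true power only if the correlation is zero.

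Section 2.3 relies on these powers to support cutting the recruitment target to 70,000 and moving to 1:3 allocation. If they were calculated for a different design, the case for both decisions is stated more favourably than the protocol's own design allows. This matters most where the calculation leaves no reserve.

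**Working it through.** **Inputs.** Arm sizes are from Table 1 (control / intervention): 25,625 / 36,875 at 1,500 per month and 27,500 / 42,500 at 2,000 per month. Rates are from sections 2.3 and 2.4. The test is two-sided at 5%, so z = 1.96.

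**Step 1: reproduce the stated powers with independent women.**

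Unpooled: power = Φ(d/s₁ − 1.96), where d is the rate difference and s₁ = √[p₁(1−p₁)/n₁ + p₂(1−p₂)/n₂].

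Pooled: power = Φ((d − 1.96·s₀)/s₁), where s₀ uses the pooled rate in both arms.

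Detection at 1,500 per month: d = 0.002, s₁ = 0.000716, s₀ = 0.000733.
- Unpooled: 0.002/0.000716 − 1.96 = 0.832, so power is 79.7%.
- Pooled: (0.002 − 1.96 × 0.000733)/0.000716 = 0.788, so power is 78.5%.

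| Comparison | Stated | Pooled | Unpooled |
|---|---|---|---|
| Detection, 9 v 7, 1,500/month | about 80% | 78.5% | 79.7% |
| Detection, 9 v 7, 2,000/month | >80% | 82.3% | 83.7% |
| Interval, 3.5 v 2, 1,500/month | >90% | 94.2% | 93.0% |
| Second round, 8 v 6, 1,500/month | >80% | 84.2% | 83.0% |

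The stated figures therefore match individual randomisation with no allowance for clustering.

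**Step 2: apply a design effect (DE).** DE = 1 + (m − 1) × ICC, where m is the number of women per randomised unit. Both variances are multiplied by DE. The protocol gives neither m nor ICC, so the DE values below are assumed. Entries are pooled / unpooled power.

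| DE | Detection 1,500 | Detection 2,000 | Interval 1,500 | Second round 1,500 |
|---|---|---|---|---|
| 1.05 | 76.4 / 77.8% | 80.4 / 81.9% | 93.2 / 91.9% | 82.4 / 81.1% |
| 1.10 | 74.5 / 75.9% | 78.5 / 80.1% | 92.1 / 90.6% | 80.7 / 79.3% |
| 1.20 | 70.7 / 72.2% | 74.9 / 76.6% | 89.8 / 88.1% | 77.3 / 75.8% |

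**Step 3: the DE at which each claim fails.** Unpooled: DE = [(d/s₁)/(1.96 + z_power)]², where z_power is 0.842 for 80% and 1.282 for 90%. For interval cancers this is [3.439/3.242]² = 1.13. The pooled version is [d/(1.96·s₀ + z_power·s₁)]².
- Detection, 1,500 per month, 80%: 0.96 pooled, 0.99 unpooled. Both are below 1, so there is no reserve.
- Detection, 2,000 per month, 80%: 1.06 pooled, 1.10 unpooled.
- Second round, 80%: 1.12 pooled, 1.08 unpooled.
- Interval, 90%: 1.19 pooled, 1.13 unpooled.

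**Step 4: what DE is plausible?** For a rare outcome with rate p and between-clinic coefficient of variation CV, ICC ≈ CV² × p/(1 − p). Assume CV = 0.3.
- Detection, p = 0.008: ICC = 0.09 × 0.008/0.992 = 0.00073. For m = 20 to 50, DE = 1.01 to 1.04. For m = 100 to 200, DE = 1.07 to 1.14.
- Interval cancers, mean rate near 2.6 per 1000: ICC = 0.00023. For m = 20 to 50, DE is at most 1.01.

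On these assumptions, a unit of 20 to 50 women costs detection power a point or two. A unit of 100 to 200 puts the 2,000 per month detection claim at or below 80%. Whether the unit is a clinic or a batch therefore matters.

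**The case against.** The strongest reply is that the loss may be trivial. Outcomes of 2 to 9 per 1000 carry very small ICCs and a single clinic may be small. At a DE of 1.05 the interval, second-round and 2,000 per month claims all survive. The Introduction places the clinic randomisation within each site, so differences between sites are largely balanced across the arms. For detection at 1,500 per month the protocol claims only approximate 80% power, which a fall of a point or two barely contradicts. All of this stands. It limits the size of the problem, but it does not supply the missing allowance or a reason for omitting one.

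Several stronger readings are tempting, and the documents do not support them:
- **That the 80% and 90% powers are not delivered.** This depends on a cluster size and an ICC that the protocol does not give. For most of the claims it is not shown.
- **That the analysis ignores clinics and inflates type I error.** The protocol does not commit the primary comparisons to an unadjusted method, and the statistical analysis plan, not seen here, may specify one that allows for clinic.
- **That the economic bootstrap resamples individual women.** Section 2.5 says only "The trial data will be bootstrapped" and names no resampling unit.
- **That consent follows the clinic's arm.** Clinics are allocated in advance and some women consent late, but nothing says that staff or women know the arm before consent. The 26%–81% participation range is between sites, and the protocol attributes it to local demographics. It is not evidence of a difference by arm.

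**Conclusion.** The point holds as a mismatch between the design and the power calculation. Sections 2.2 and 4.2 randomise clinics or batches, while the powers in sections 2.3, 2.4 and 3 are those of an individually randomised trial.

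The clear consequence is for the first primary endpoint at the lower recruitment rate. It sits at or just under 80% before clustering, and any design effect above 1 lowers it further. The other three claims have some reserve and fail only beyond the break-even values in the working.

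The reproduction and the break-even values follow from the protocol's own figures. Which design effect applies rests on assumed cluster sizes and ICCs. With small clinics and a low ICC the practical loss is a point or two, so this is a should-fix.

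**What to change.** 1. State whether the randomised unit is the clinic or the batch, and take its mean size from the more than 36,000 women already recruited.
2. Assume an ICC range separately for each endpoint. An ICC estimated from trial data would be imprecise: 36,000 women at 8 per 1000 is about 290 cancers, spread thinly over many clinics.
3. Restate the powers in sections 2.3, 2.4 and 3 with the resulting design effects, at both recruitment rates where both are quoted.
4. Confirm, in the protocol or by reference to the statistical analysis plan, that the primary comparisons allow for clinic.

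The cost is a short calculation and some wording. Stated power becomes slightly less favourable, and the correction itself requires no extra women.

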2.4 Trial Statistics

1. Impact of DBT on breast cancer deaths

The trial was originally conceived to show a difference between study and control groups in interval cancer rates. However, there is a clear need for a result indicating the additional benefit of DBT screening before the interval cancers are observed. We propose to base formal significance testing at this earlier stage on the harvest of invasive cancers detected at screening and on the pathological size of these cancers. In order to avoid overestimation of the likely benefit from over diagnosis or length bias, we will test for a difference in size between the Grade 2 and 3 cancers detected by DBT and 2DDM compared to 2DDM. A preliminary estimate of the effect of DBT on reducing breast cancer deaths compared to standard 2DDM will be calculated using the difference in cancer detection rates and the prognostic features of the screening detected cancers in the study group (DBT + 2DDM or S2D) compared to the control group (2DDM). This will be calculated using only the invasive grade 2 and 3 cancers to give a conservative estimate, and then using all cancers, potentially giving an anticonservative estimate. The true effect is likely to lie between the two. At three to five years following recruitment, the interval cancer rates will be compared between the two groups. Thereafter, a more definitive estimate of the expected breast cancer deaths avoided will be calculated using both screen-detected and interval cancers. Projected mortality will be estimated using the approaches developed by Day and Duffy (1996), Duffy et al (1997) and Chen et al (1997).

2. Universal FFDM only at second round

Again, due to pressures on resources and capacity, specifically screening time, it is unlikely to be feasible that a second round of DBT can take place in the subjects in the intervention arm. We therefore propose that the second round in both arms be with the standard of care in the NHSBSP, FFDM alone. This may in fact have an unexpected benefit. If the harvest of cancers at the second round is lower in the

intervention arm, this will establish that DBT results in detection of cancers that would have been diagnosed with the standard of care in any case but would have been detected three years later, likely at a substantially later stage.

We assume that the yield of cancers in the control group will be 8 per thousand as previously observed in the NHSBSP (more recent figures suggest closer to 9 per thousand, but we work with 8 per thousand to be conservative). We might reasonably expect this to be 6 per thousand in the intervention arm due to increased prior detection rates with DBT. With 36,875 women in the intervention arm and 25,625 in the control arm, we will have more than 80% power to detect such a difference as significant (5% significance, 2-sided testing). Thus, even with the conservative assumption of 1,500 recruitment per month, the study will be adequately powered for this comparison.

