3.2 Exclusion Criteria

- Women aged less than 49 years or more than 71 years (these women may already be taking part in the National Age Extension Screening Trial)
- Women unable to provide informed consent.

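### Second-round power is computed on everyone recruited at round 1, with no allowance for women not re-screened three years later, so the claim of more than 80% is conditional

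*Protocol*

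**What the plan says.** Section 2.4 (item 2, on standard mammography in both arms at the second round) plans to compare the yield of cancers at the next screen, three years after the trial screen. The inputs are:

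- Control yield: "We assume that the yield of cancers in the control group will be 8 per thousand as previously observed in the NHSBSP". On the choice of 8 it adds: "more recent figures suggest closer to 9 per thousand, but we work with 8 per thousand to be conservative".
- Intervention yield: "We might reasonably expect this to be 6 per thousand in the intervention arm due to increased prior detection rates with DBT".
- Numbers and power: "With 36,875 women in the intervention arm and 25,625 in the control arm, we will have more than 80% power", at two-sided 5%.
- Conclusion: "Thus, even with the conservative assumption of 1,500 recruitment per month, the study will be adequately powered for this comparison".

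Table 1 (section 2.3, repeated in section 3) has the same 25,625 and 36,875 in its 1,500-per-month row. Its title is "Estimate of numbers recruited in control and intervention groups to 03.2025, with a 1:3 randomization ratio from 01.2024".

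On who might be lost, section 3.1 admits women aged 49-71. Section 3.2 excludes "Women aged less than 49 years or more than 71 years" and remarks that such women may be in a separate age extension trial. Section 3.3 foresees no premature withdrawal. The Protocol gives no second-round attendance rate, no age distribution of recruits and no upper age for second-round screening.

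**The concern.** The yield at the second round is a rate per woman screened at that round, so its denominator is the number who come back. The Protocol uses the number recruited. Some loss over three years is certain. Women at the top of the entry range will be 72-74, some cancers will already have been diagnosed, and some women will move, die or not attend.

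What is at stake is how the comparison is read. Section 2.4 gives it a specific role: a lower second-round harvest after DBT would show that DBT had brought forward cancers that standard screening would have found later. If power is lower than stated, a null result is more likely even when that effect is real, and a reader who trusts the printed figure would give the null too much weight.

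**Working it through.** **Inputs.** p1 = 0.008 (control) and p2 = 0.006 (intervention), two-sided 5% (z = 1.96), section 2.4. Table 1 gives n1 = 25,625 and n2 = 36,875 at 1,500 per month, and 27,500 and 42,500 at 2,000 per month.

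**Formulae** (normal approximation, d = p1 − p2 = 0.002):

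- S1 = √[p1(1−p1)/n1 + p2(1−p2)/n2]
- S0 = √[p̄(1−p̄)(1/n1 + 1/n2)], where p̄ is the average of p1 and p2 weighted by arm size
- Unpooled power = Φ(d/S1 − 1.96)
- Pooled power = Φ((d − 1.96·S0)/S1)

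**Step 1: reproduce the stated figure.** At 1,500 per month, S1 = 0.0006866, p̄ = 0.00682 and S0 = 0.0006693.

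- Unpooled: Φ(2.913 − 1.960) = Φ(0.953) = 83.0%.
- Pooled: Φ((0.002 − 0.001312)/0.0006866) = Φ(1.002) = 84.2%.

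Both exceed 80%, so the printed figure is right for these inputs. At 2,000 per month the values are 86.3% and 87.5%.

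**Step 2: loss implied by the Protocol's own rates.** From section 2.3, invasive cancers at round 1 plus interval cancers come to 7 + 3.5 = 10.5 per 1000 in control and 9 + 2 = 11 per 1000 in intervention. About 1.1% would therefore already have a diagnosis. By itself this lowers power only to 82.6% (unpooled) or 83.8% (pooled) at 1,500 per month.

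**Step 3: break-even.** Multiply both arms by the share f re-screened and solve for 80% power.

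| Recruitment | f, unpooled | f, pooled | Loss that can be absorbed |
|---|---|---|---|
| 1,500/month | 92.5% | 89.3% | 7.5% to 10.7% |
| 2,000/month | 84.2% | 80.7% | 15.8% to 19.3% |

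**Step 4: illustrations.** These retention rates are assumptions. The first row is the stated case. The second takes entry ages as uniform over the 23 years from 49 to 71 and supposes that nobody aged 69-71 at entry is re-screened, so f = 20/23 = 87%. The last two apply 95% and 85% attendance to the rest: 0.87 × 0.95 = 0.83 and 0.87 × 0.85 = 0.74.

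| Share re-screened | 1,500/month, unpooled to pooled | 2,000/month, unpooled to pooled |
|---|---|---|
| 100% | 83.0% to 84.2% | 86.3% to 87.5% |
| 87% | 77.5% to 79.0% | 81.3% to 82.8% |
| 83% | 75.4% to 76.9% | 79.3% to 80.9% |
| 74% | 70.7% to 72.4% | 74.7% to 76.5% |

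**Step 5: is 8 per 1000 conservative?** All women returning, 1,500 per month:

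| Control v intervention, per 1000 | What is held fixed | Power, unpooled to pooled |
|---|---|---|
| 8 v 6 | as stated | 83.0% to 84.2% |
| 9 v 7 | absolute fall of 2 per 1000 | 77.9% to 79.2% |
| 9 v 6.75 | relative fall of 25% | 87.1% to 88.1% |

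Moving from 8 to 9 lowers power under the absolute reading and raises it under the relative one.

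**The case against.** The strongest reply is that the calculation is correct on its stated inputs and that the documents do not give the loss. This stands. A reader might infer that the 80% claim fails on the Protocol's own numbers, or that the true power is some fixed figure in the seventies. The documents support neither. The shortfall depends on a retention rate that they do not state.

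A reader might also infer that every woman aged 69-71 at entry drops out. Sections 3.1 and 3.2 set ages for trial entry only, the second round is routine care, and section 3.2 itself mentions screening beyond 71 under another trial. The 87% figure is therefore an illustration. At 2,000 per month that case stays above 80% by both formulae, and the 83% case does so by the pooled one.

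A third tempting inference is that 8 per 1000 was the favourable choice. It is so only if the absolute fall is kept. Attributing the fall to earlier detection, with a posited round-1 gain of 2 per 1000 (9 v 7), makes that reading plausible. But section 2.4 does not say so, and with the 25% relative fall kept, 8 is conservative as claimed.

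Finally, second-round yield is not a listed primary or secondary end-point, and recruitment was not sized on it. That limits the importance of the point. It does not remove it, because the Protocol itself prints the numbers, the power and the conclusion that power is adequate.

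**Conclusion.** The point holds in a conditional form. The stated power uses recruitment totals as if they were second-round screens, so it requires 100% re-screening, and nothing in the Protocol supports that. The margin is thin in the very scenario for which adequacy is claimed: at 1,500 per month a loss above about 7.5% to 10.7% removes it, depending on the variance formula. At 2,000 per month it takes about 16% to 19%.

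Under the assumed 74-83% re-screened, power is about 71-77% at 1,500 per month and 75-81% at 2,000. These ranges rest on uniform entry ages, no re-screening after 71, 85-95% attendance among the rest, and equal loss in both arms. The fault lies in an unstated assumption about the denominator, and the arithmetic itself is sound. The conservative label on 8 per 1000 is unsupported until the Protocol says which effect is held fixed.

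**What to change.** Rewrite the power paragraph of section 2.4, item 2:

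- Give the expected number of second-round screens per arm: recruits still eligible at the second round, multiplied by expected attendance. Estimate both from NBSS data on the women already recruited (over 36,000 by September 2023).
- State up to what age women are expected to be re-screened.
- Show power over a range of retention for both recruitment scenarios, and name the test.
- Replace the unconditional statements of more than 80% and of adequate power with that range.
- Say whether the 2 per 1000 or the 25% reduction is held fixed when the control rate is 9 per 1000, show both rates, and keep the conservative label only if the relative reduction is meant.

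The cost is one paragraph, one data extract and a slightly less favourable stated power. No participants are added and the design does not change.
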